3.4 Participant onboarding

3.4.1 Allocation of devices

Once participants have provided their consent, each will receive a phone call from Optima Systems Ltd to:

- Ensure the information provided is correct
- Check that the participant is still happy to proceed
- Reiterate the key points of information provided in the Participant Information Sheet
- Establish the current technical capability of each participant i.e. WiFi connectivity

We intend to choose the most suitable smart technology for each patient. The choice of the smart technology is based on careful judgement and we will aim to develop an approximate "right app or wearable for the right patient" as clearly as we can. We will do this based on the initial conversation held with the participant.

Since patients do not necessarily become ill with the same conditions they already have, one or at most two devices per patient will be chosen. We are aiming to include about a third of the patients from residential and care homes since they will tend to be more vulnerable and more likely to have an adverse health event and certain apps can be used by smart devices can be installed from the internet.

The questionnaires will be sent and completed by the patient on the smart phone, tablet or desktop. We currently are considering how we can safely use the same tablet in a Care home to obtain clinical information on respiratory and heart rate and BP oxygen saturation on several patients. This will involve engaging with the residential and care home staff to develop safe procedures; this will be helped by the knowledge of the Covid-19 status of both patients and staff in terms of blood antibody tests on all the staff and all the patients. We hope also that the availability of PPE (Personal Protective Equipment) will be confirmed in each of the relevant homes.

The next action will be to arrange for the participants to receive the wearable or smart technology and to be shown how to use it by the "research supporter" with the aid of the internet. We will be allocating participants randomly according to their circumstances, to receive two (or at most three) wearables or smart technologies.

Commented [CP3]: Updated slightly as we have concluded device allocation will be random to an extent – please ensure my wording is accurate here

Commented [**CP4**]: I think we should go further here and propose a process otherwise it is quite a big question mark this will link back to the SOP you are developing [name].

Commented [**CP5**]: Can we say – "Optima will then post devices and instructions on how to use them to participants. As soon as the participant receives their devices they will be able to start using them to take health measurements straight away. If a participant has any difficulty in using their devices, they will be able to call Optima Systems for support and guidance".

IRAS ID: 286225 CPMS: 44344 01/08/2020 [Proof of Concept – Smart Technology – South Lincolnshire] PoC Protocol Version: 1.4 15

Device / App name	Physiological measurement	Characteristics of	device / app	Participants
LifeLight	 Respiratory & heart rate, BP & pO₂ 	Digital camera on iPad		As many as possible – proportion shared in Care homes – readings daily
Thermometer	Temperature	Hand held the	rmometer	All participants for 6 days/week
FibriCheck	• ECG – (FIBRICHECK)	Visual Plethysn	nography	300 participants – daily readings
Device / App name	Behavioural	measurements		
GENEactive	 Activity inter 	Activity intensity / duration &		500 participants
Band	frequency/ sleep quality			Daily readings
QuestLink	 Mental, social and physical health status and progression. Measures of patient self-confidence (HCS) and Health Status (howRU) 		All participan	ts - on average twice weekly

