3.1 Participant eligibility

The research team aim to recruit 500 participants to take part in the study. In order to achieve this target number, the research team aims to identify at least 700 potential participants according to the following inclusion and exclusion criteria.

Inclusion Criteria

- Individuals over the age of 18 that:
 - Have 3 or more long-term conditions AND/OR
 - Have a medium to high frailty score AND/OR
 - Are suffering from unsteadiness or falls AND/OR
- Those who are found to have paroxysmal and/or asymptomatic atrial fibrillation (AF), hypertension or heart failure
- Live in their own homes or in residential care homes or in nursing care homes

Exclusion criteria

- Children
- Individuals for whom consent cannot be obtained (i.e. individuals with severe mental impairments or learning difficulties)
- Patients on palliative care
- Individuals lacking mental health capacity or whose mental health conditions might be influenced by participating in the study?
- Individuals who's mental capacity deteriorates during the study period will be removed from the study.

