- agree to take part in the study and undertake the required study activities (i.e. take your own health readings and/or wear a comfortable Smart Device over the period of the study which will securely record data about your health)
- are happy for your data to be collected, used, shared and stored as described in this information sheet
- understand you will not gain any particular benefit from taking part, but may be helping others in the future

Consent forms will be returned by post to Optima Systems. Optima Systems are responsible for generating the unique ID number for you for the purposes of the research. This ensures that all the data collected from participants will be pseudonymised.

Optima Systems will call the participant upon receipt of their consent forms to check all the information provided is correct and undertake a technical assessment to establish which equipment needs to be sent to the participant. Although device will be allocated at random, the research team will need to understand the connectivity and infrastructure available.

Optima Systems will then inform the participants GP that they have been onboarded to the study and ask the GP practice to cross check the information collated on the consent form to ensure that only invited participants are included. This will also help GP practices manage recruitment lists and remove anyone who has not consented from the study and any future recruitment rounds.

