3.4.2 Participant training

The first action will be to ensure that the participant understands that during the study we want to keep life as normal as possible for them. There will be no new drugs being tested, no special behaviours asked of them, and no medical tests to be done and no additional consultations needed.

We will be just recording data and collecting it from your wearable or smart technology supplied to them. Participants healthcare will carry on as usual with their GP and healthcare professionals and the medications that they are taking will be managed as normal by them.

The second action will be to arrange for the participant to receive the wearable or smart technology and to be shown how to use it by their "research supporter". We will be allocating participants randomly according to their circumstances, to receive two (or at most three) wearables or smart technologies. Education in its use will also be started and this will also explore how we can minimise any inconvenience for you. Pamphlets and other information will be given to the participant as well as contact numbers. Depending on the IT connectivity at home it may rarely be necessary to make arrangements to meet to participant to download the stored data on the wearable or smart technology. The participant will be well supported with support on offer during the trial by messaging electronically, or by phone and speaking to one of our helpers.

Commented [CP6]: Have removed two paragraphs here

Commented [CP7]: [name], can we discuss this paragraph -

16

IRAS ID: 286225 CPMS: 44344 01/08/2020

[Proof of Concept – Smart Technology – South Lincolnshire] PoC Protocol Version: 1.4

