3.4.3 Ongoing participant support

The participants will be supported for the trial by phone or email and speaking to one of our support staff at Optima. The support staff will also identify problems if there were a change in data flow from the devices from the participant, and seek to resolve them.

4. Smart Technologies

Each participant will be issued with one or more smart technology which will not disturb their day to day activities over the period of the study; during this period of time they will receive uninterrupted health care.

To gather meaningful information within the budget and time available, we need as large a sample size as possible which will also minimise the costs [of wearables]; it will facilitate the eventual solution economically scaling up to meet the rapidly growing and aging population. To meet the potential for scale, we will use a smart technology solution that is scalable and collects data from participants as passively and non-invasively as possible. This can involve looking at the camera on a tablet computer for thirty seconds or placing a finger over the camera on a smart phone for thirty seconds twice daily over the period of the programme. These smart technologies generate large volumes of raw data which will be pre-processed to identify discrete events or clinically meaningful and relevant measures.

The choice of the apps and wearables for an individual participant is carefully judged. We aim to achieve the "right app or wearable for the right patient" as accurately as we can. Since patients do not necessarily become ill with the same conditions they already have, apps may be chosen that do not relate to existing conditions. We will choose about a third of our participants from those who reside in a nursing care home and residential homes since they will tend to be sicker and more likely to have "an event" that may become predictable with the data collected. And also because some of our chosen apps can be used on more than one participant in a care home setting, this will provide coverage of participants with apps.

We believe the above approach to proven smart technologies will enable:

{i} Detection - of risk factors or undiagnosed conditions

{ii} **Protection** - from long term conditions by mitigation of risk through various interventions including social prescribing

{iii} Correction of conditions - many physical and chronic conditions are either reversible or the progress of the condition can be slowed

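### Device allocation is stated both as judgement and as random, with conflicting limits per participant, and whether the device table fits those limits depends on an undefined count of devices

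*Protocol*

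**What the plan says.** **Method of allocation.**
- Section 3.4.1: "The choice of the smart technology is based on careful judgement", made from the first conversation with the participant. The opening of Section 4 repeats that the choice is judged for each individual.
- Section 3.3.2: "Although device will be allocated at random", with a note that connectivity must be known.
- Section 3.4.1, further down: "We will be allocating participants randomly according to their circumstances, to receive two (or at most three) wearables or smart technologies". Section 3.4.2 repeats this.
- A margin comment left in Section 3.4.1 calls allocation random to an extent and asks for the wording to be checked.

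**Number per participant.**
- Section 3.4.1: "one or at most two devices per patient will be chosen".
- Sections 3.4.1 and 3.4.2: "to receive two (or at most three) wearables or smart technologies".
- The end of Section 1.3 and the opening of Section 4: one or more, with no upper limit.

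**Device table in Section 3.4.1.** Thermometer for all, activity band for 500, QuestLink for all, FibriCheck for "300 participants – daily readings". LifeLight has no number: as many as can be managed, partly shared in care homes, read daily.

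**Frequency.** The table has both camera apps read daily. Section 4 describes "placing a finger over the camera on a smart phone for thirty seconds twice daily over the period of the programme".

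**The concern.** Who carries which sensor is part of the design, and the contractor that ships the devices cannot follow these instructions as they stand. One person might be judged to need a given app, might be drawn for it by chance, or might already be at one limit but not at the other.

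The stake is the prediction question. The study wants to know whether device signals foretell adverse events. About a third of participants are to come from care homes, explicitly because events are thought more likely there, and LifeLight is partly tied to shared use in those homes. The mere presence of LifeLight data may therefore mark setting, and setting marks risk. If individual judgement decides, the presence of FibriCheck or LifeLight data may mark illness too. A model could then draw on who holds the app rather than on what the app records. If the reasons for allocation were not recorded when devices were issued, later analysis cannot recover them.

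**Working it through.** **Inputs.** "The research team aim to recruit 500 participants to take part in the study" (Section 3.1), so N = 500. Table targets: band 500, thermometer 500, QuestLink 500, FibriCheck 300, LifeLight unnumbered (0 to 500). Limits: 2 or 3 per participant, giving 2 × 500 = 1,000 or 3 × 500 = 1,500 places.

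The protocol does not define a device, so three counts are tried. Total before LifeLight = sum of the counted targets; mean = total / 500. FibriCheck splits the sample into 300 holders and 200 others.

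| Items counted | Total before LifeLight | Mean | Held by the 300 | Held by the 200 |
|---|---|---|---|---|
| (a) All five rows | 500 + 500 + 500 + 300 = 1,800 | 3.6 | 4 | 3 |
| (b) Without QuestLink | 500 + 500 + 300 = 1,300 | 2.6 | 3 | 2 |
| (c) Band, FibriCheck, LifeLight only | 500 + 300 = 800 | 1.6 | 2 | 1 |

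If every participant also had LifeLight, the means would be 4.6, 3.6 and 2.6.

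**Against a limit of 2.**
- (a) All 500 are over; 1,000 − 1,800 = −800 places.
- (b) The 300 FibriCheck holders are over; 1,000 − 1,300 = −300. No room for LifeLight.
- (c) Nobody is over; 1,000 − 800 = 200 places remain, all among the 200 without FibriCheck. LifeLight is at most 200 and nobody has both apps.

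**Against a limit of 3.**
- (a) The 300 FibriCheck holders are over; 1,500 − 1,800 = −300. No room for LifeLight.
- (b) Nobody is over; 1,500 − 1,300 = 200 places remain, again all among the 200 without FibriCheck. LifeLight is at most 200 with no overlap.
- (c) Nobody is over; 1,500 − 800 = 700 places remain. All 500 can have LifeLight, and all 300 FibriCheck users can have both.

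**Which signals are exposed.** Band, thermometer and QuestLink go to everyone, so having them cannot depend on illness or setting by allocation. FibriCheck goes to 300 / 500 = 60% and LifeLight to an unstated share, so only these two can. The care-home share is about 500 / 3 ≈ 167 participants.

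**Frequency.** Section 1.3 gives approximately six months. Taking 26 weeks as an assumption, daily is 26 × 7 = 182 readings and twice daily is 2 × 182 = 364.

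**The case against.** The strongest reply is that the limits were never meant to cover everything in the table. Section 4.1 describes temperature entry as part of QuestLink, and a questionnaire is hardly a wearable. On that reading only the band, FibriCheck and LifeLight count, and a limit of three accommodates the whole table. This stands. A reader might infer that the table fits no stated limit, or that rhythm and vital signs can never be observed in the same person. Neither follows, because both depend on a count that the protocol leaves open.

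It can also be said that confounding is only a possibility. No section links FibriCheck to sicker people or to care homes. Section 4 says that apps may be unrelated to existing conditions, Section 3.3.2 asks about connectivity rather than illness, and the shared tablet in care homes is still under consideration. This stands in part: it weakens the illness path, but not the link between LifeLight and setting. Nor would it be right to object that devices could not be compared with one another, since Section 2.1 does not make that an aim. How models adjust for setting can be left to the analysis plan.

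Finally, judged allocation is a legitimate choice in an observational proof of concept if it is stated and logged. That is true, but the protocol states it alongside its opposite. The frequency conflict is minor, because the sentence in Section 4 is worded as an illustration.

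**Conclusion.** The point holds as a contradiction in current text. There are two allocation methods and three statements of number per participant, and there is no definition of a device. This needs no assumption beyond reading the sections together.

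The misfit with the table is conditional. Both limits are broken if all five rows count (3.6 items each before LifeLight), and only the limit of two if QuestLink is left out (2.6 each). Neither is broken if only the band, FibriCheck and LifeLight count (1.6 each), although a limit of two then restricts LifeLight to 200 participants, none of them with FibriCheck. These counts assume that 500 are recruited and that the table targets are met exactly.

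Confounding is a risk, not a certainty, and is confined to two apps. It is best supported for LifeLight through care-home setting. For illness it arises for FibriCheck or LifeLight only if judgement decides. A reader might extend it to every signal, but the items given to all participants rule that out. The daily versus twice-daily wording is a real but small inconsistency.

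**What to change.** Reconcile the end of Section 1.3, Sections 3.3.2, 3.4.1 (text and table) and 3.4.2, and the opening of Section 4, before devices are issued:

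- Define what counts as a device, saying explicitly whether the thermometer, QuestLink and shared use of a tablet are included.
- Keep band, thermometer and QuestLink for all, and replace the limits with one number that agrees with the table. To let a participant hold everything, that number is 5 on count (a), 4 on (b) and 3 on (c).
- State one allocation method. Section 3.3.2 and the margin comment already lean towards chance, so draw the 300 FibriCheck places at random within setting (own home or care home) among technically able participants. Do the same for LifeLight wherever a compatible device exists. Amend the sentences on individual judgement to match.
- Record the reason for every allocation that is not random.
- State one reading frequency for the camera apps.

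The cost is protocol wording, a simple random list for the contractor and a reason field in its log. The price in practice is less freedom to choose devices case by case.

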3.4.2 Participant training

The first action will be to ensure that the participant understands that during the study we want to keep life as normal as possible for them. There will be no new drugs being tested, no special behaviours asked of them, and no medical tests to be done and no additional consultations needed.

We will be just recording data and collecting it from your wearable or smart technology supplied to them. Participants healthcare will carry on as usual with their GP and healthcare professionals and the medications that they are taking will be managed as normal by them.

The second action will be to arrange for the participant to receive the wearable or smart technology and to be shown how to use it by their "research supporter". We will be allocating participants randomly according to their circumstances, to receive two (or at most three) wearables or smart technologies. Education in its use will also be started and this will also explore how we can minimise any inconvenience for you. Pamphlets and other information will be given to the participant as well as contact numbers. Depending on the IT connectivity at home it may rarely be necessary to make arrangements to meet to participant to download the stored data on the wearable or smart technology. The participant will be well supported with support on offer during the trial by messaging electronically, or by phone and speaking to one of our helpers.

Commented [CP6]: Have removed two paragraphs here

Commented [CP7]: [name], can we discuss this paragraph -

16

IRAS ID: 286225 CPMS: 44344 01/08/2020

[Proof of Concept – Smart Technology – South Lincolnshire] PoC Protocol Version: 1.4

3.4.3 Ongoing participant support

The participants will be supported for the trial by phone or email and speaking to one of our support staff at Optima. The support staff will also identify problems if there were a change in data flow from the devices from the participant, and seek to resolve them.

4. Smart Technologies

Each participant will be issued with one or more smart technology which will not disturb their day to day activities over the period of the study; during this period of time they will receive uninterrupted health care.

To gather meaningful information within the budget and time available, we need as large a sample size as possible which will also minimise the costs [of wearables]; it will facilitate the eventual solution economically scaling up to meet the rapidly growing and aging population. To meet the potential for scale, we will use a smart technology solution that is scalable and collects data from participants as passively and non-invasively as possible. This can involve looking at the camera on a tablet computer for thirty seconds or placing a finger over the camera on a smart phone for thirty seconds twice daily over the period of the programme. These smart technologies generate large volumes of raw data which will be pre-processed to identify discrete events or clinically meaningful and relevant measures.

The choice of the apps and wearables for an individual participant is carefully judged. We aim to achieve the "right app or wearable for the right patient" as accurately as we can. Since patients do not necessarily become ill with the same conditions they already have, apps may be chosen that do not relate to existing conditions. We will choose about a third of our participants from those who reside in a nursing care home and residential homes since they will tend to be sicker and more likely to have "an event" that may become predictable with the data collected. And also because some of our chosen apps can be used on more than one participant in a care home setting, this will provide coverage of participants with apps.

We believe the above approach to proven smart technologies will enable:

{i} Detection - of risk factors or undiagnosed conditions

{ii} **Protection** - from long term conditions by mitigation of risk through various interventions including social prescribing

{iii} Correction of conditions - many physical and chronic conditions are either reversible or the progress of the condition can be slowed

4.1 Our chosen wearables, sensors and monitors

The core of our chosen solutions are highly innovative and include the following:

LifeLight from XIM is a contactless solution and is certified for the Apple iPad with a built-in camera and a smart phone with IoS or Android with a camera. The iPad based smart technology (LifeLight from XIM) allows measurement of four vital signs (heart rate, blood pressure, oxygen saturations and respiration) in just 30 seconds using a standard Apple iPad, with no additional hardware. Lifelight[®] is a software application (app) which allows completely non-invasive and non-contact measurements. It has satisfied the essential requirements of the Medical Device Directive (94/42/EEC) for CE marking.

17

FibriCheck from Qompium will be used to measure ECG and to detect heart irregularities, as this is the only medical grade CE certified (class IIa) application to detect cardiac arrythmias using only a smartphone with no additional hardware or device. FibriCheck has been validated in several clinical studies compared to the gold standard 12 lead ECG. FibriCheck has a similar diagnostic accuracy compared to Alivecor single-lead ECG. FibriCheck is certified as a Class IIa product and is Certified under Directive 93/42/EEC and all software is compliant to ISO62304 – Medical device software. Other applicable standards include : EN ISO 980:2008 Symbols for use in the labelling of medical devices; EN 1041:2008 Information supplied by the manufacturer of medical devices and Good clinical practice (ISO 14155:2011).

GENEactive Band produces raw data real time with real time output. A further aspect of our hypothesis calls for the measurement of activity and quality of sleep, as life-style is one the most important factors in the prevention, treatment, and management of many long-term conditions. Since 2008 Activinsights have used lifestyle insights from wearables and connected devices to digitally support healthcare services in over 40 countries around the world. Active insights technologies and data analysis approaches are supported by over 300 peer-reviewed scientific papers. Products are made in the UK to ISO 13485. The GENEactive band is not a Medical Device and is not currently registered with MHRA. In view of the changed regulations in 2020 the Activeinsights registration is in the process of being developed.

QuestLink enables surveys to be automatically scheduled and distributed to the participants devices. This will include measures of participants self-confidence (Health Confidence Score) and Health Status (howRU) for participants with multimorbidity; mental health, social and physical health status, and progression; current medication and changes and others. It will also include the use of a handheld thermometer to enter the temperature 6 times a week.

TABLE B – Measurement details, devices and details of device/app

Physiological measurement	Device / App name	Characteristics of device / app
Respiratory rate	LifeLight	Digital camera on iPad
Oxygen saturation	LifeLight	Digital camera on iPad
Blood pressure	LifeLight	Digital camera on iPad
Temperature	Thermometer	Hand held thermometer
• ECG – (FIBRICHECK)	FibriCheck	Visual Plethysmography

Behavioural measurements	Device / App name	Characteristics of device / app
Activity intensity / duration & frequency	ActivInsights Band	Wearable Band
 Sleep / Circadian cycle / Sleep time and duration & quality 	ActivInsights Band	Wearable Band
Acceleration monitor for bone health	ActivInsights Band	Wearable Band

18

IRAS ID: 286225 CPMS: 44344 01/08/2020 [Proof of Concept – Smart Technology – South Lincolnshire]

PoC Protocol Version: 1.4

Rehabilitation balance and safety in falls patients	ActivInsights Band	Wearable Band
• Mental, social and physical health status and progression. Measures of patient self-confidence (HCS) and Health Status (howRU)	QuestLink	Cloud based Response to questions – personalised and automatically scheduled and distributed to participant devices

Environmental & Social determinants of health		
Air quality - pollutants	Sensor Related to postal code	Static – accessed from "public sites"
Postcode or GP Postcode –	First digits of postcode	Static data
Lincolnshire Research Observatory (LRO)	Index of Multiple Static – accessed from "public sites Deprivation (IMD)	

